2.0	14th Feb 2022	
Amendment submitted to the HUS ethical committee.
 
 • CIP restructured to be compliant with REGULATION (EU) 2017/745 OF THE EUROPEAN PARLIAMENT AND OF THE COUNCIL of 5 April 2017 on medical devices, amending Directive 2001/83/EC, Regulation (EC) No 178/2002 and Regulation (EC) No 1223/2009 and repealing Council Directives 90/385/EEC and 93/42/EEC. • Restructured the CIP headings to clarify the content. • Renamed the appendix for clarity. • The questionnaires are updated as follows: Restructured questionnaires: demography and care status. Removed: BDI, OASIS, BAI, MSI-BDP, SHAPS. Added: QIDS-SR16, GAD7, RRS, PVSS, ASSIST-LITE, BEAQ, SDS, WHO-5, GAS, and IEQ. • Added treatment-as-usual (TAU) group as a third study arm. • Clarified the distinction between MEL-T01 and MEL-S01. • Added a qualitative, experiential interview to complement the quantitative data collection. • The targeted number of subjects decreased from $N = 1000$ to $N = 800$ according to the new power calculation. • Added an interim analysis. • Added information that the pseudonymized data will be shared with study partners (Wellcome Leap) in the USA. This is noted in “Participant Information and Consent Form”, “Confidentiality Obligation and Right of Use” and “Privacy Notice and Impact Assessment” (Appendices 2, 3, and 4). • Clarified the legal notes about data usage in participant’s information and consent appendices. • Added a clinical interview (MINI) to confirm the subject’s MDD diagnosis. • In addition to recruiting subjects from HUS and VSSHP, online channels will also be used. • Removed brain imaging (MEG, MRI) from the main study and added it as a formal academic sub-study with TMS and EEG (using an identical protocol to one earlier approved by HUS ethical committee at Case Number: HUS-1198-2016-9) as an additional research instrument. Healthy subjects are only included in the sub-study. In the brain-imaging sub-study, the subjects are offered a possibility but no obligation to participate in a TMS study.

3.1 General

3.1.1 Single identification number of the clinical investigation

CIP identifier, CIP version, and CIP date visible on the cover page.

3.1.4 Financing of the clinical investigation

The research is funded by the following:

- **Business Finland Research2Business** funding for project "Aalto R2B Meliora" granted to Aalto University (1/2021-12/2022); 943.000 €; principal investigator [name].
 - This funding covered the development of investigational and comparator digital therapeutics devices, their backend infrastructure, and data management. The funding also covers the launching of the intervention trial with symptom questionnaires as primary and secondary endpoints.
- Technology Industries of Finland Centennial Foundation and Jane and Aatos Erkko Foundation **Future Makers funding program** for project "Using New Game Technology for Digital Therapies in the Treatment of Brain Disorders and the Maintenance of Brain Health" granted to Aalto University (1/2021-12/2023); 500.000 €; principal investigator [name].
 - This funding was used to develop the methodological basis for dynamic individualization of the investigational device and comparator to enable their use in the personalised medicine framework.
- **Wellcome Leap Multi-Channel Psych** research funding for the project "Plasticity Stimulation in the treatment of anhedonia" granted to University of Helsinki and Aalto University (12/2021-12/2024); 2.550.000 €; principal investigator [name], co-principal investigators [name], [name] and [name].
 - This funding covers behavioural phenotyping, the brain imaging and stimulation sub-study (MEG, EEG, MRI, TMS) and personalised brain modelling. This project is part of a \$55M Wellcome Leap project that aims to uncover mechanistic biomarkers for anhedonic depression, and is well positioned to yield significant breakthroughs in understanding major depressive disorder and its treatment.

The research does not cause expenses to The Hospital District of Southwest Finland (VSSHP) or The Hospital District of Helsinki and Uusimaa (HUS).

Description of the agreement between the sponsor and the site. This study is based on a collaboration agreement between sponsor (coordinating investigator) and sites. Research permits from HUS and VSSHP for the present project account for agreement between the sponsor and these research sites.

3.1.5 Abbreviations

AE	Adverse event
ASSIST-LITE	Alcohol, smoking and substance involvement screening test lite
BEAQ	Brief experiential avoidance questionnaire
CSC	Clinical subject coordinator
DTx	Digital therapeutics
EMI	Electro-magnetic interference
GAD-7	General anxiety disorder questionnaire
MEL-T01	Active investigational device in this study
MEL-S01	Active comparator device in this study
GAS	7 item game addiction scale
GCP	Good Clinical Practice
GPP	Good Programming Practices
HUS	Helsinki and Uusimaa hospital district
IEC	Institutional ethics committee
IEQ	Immersive experiences questionnaire
IRB	Institutional review board
LPFC	Lateral prefrontal cortex
MDD	Major depressive disorder
MINI	International neuropsychiatric interview
PCL-5	PTSD checklist for DSM-5
PGSI	Problem gambling severity index
PHQ-9	Patient health questionnaire
PVSS	Positive valence systems scale
QIDS-SR16	Quick inventory of depressive symptomatology
RCT	Randomised controlled trial
RRS	The ruminative response scale

SAE	Serious adverse event
SDS	Sheehan disability scale
TAU	Treatment as usual
VMPFC	Ventro-medial prefrontal cortex
VSSHP	The Hospital District of Southwest Finland
WHO-5	The World Health Organisation -five well-being index

3.1.6 Synopsis of the clinical investigation

Name of sponsor/company: Aalto University
Study identification code: MelioraRCT
Title of the study: The effects of videogames on depression symptoms and brain dynamics
Study period: Planned first subject visit: 1.3.2022. Planned study completion: 31.12.2023.
Participating countries and number of sites: Neuroscience Centre, HiLIFE, University of Helsinki, Finland. Department of Neuroscience and BioEngineering Aalto University, Finland. BioMag laboratory, HUS Medical Imaging Centre, Helsinki University Hospital, Finland. Aalto NeuroImaging Infrastructure, Espoo, Finland
Number of subjects: Main study: $N = 800$ with major depressive disorder (MDD). In addition, in the sub-study: $N = 100$ healthy adults

Study objectives:

The study is a comparator-controlled, randomised, double-blinded intervention study aimed at assessing the effects of the investigational device MEL-T01, “Meliora”, on the symptoms of major depressive disorder (MDD). MEL-S01 acts as a comparator. MEL-T01 is a game-based digital-therapeutics (DTx) medical software device developed at Aalto University and is intended to be used as a treatment for MDD together with treatment-as-usual (TAU). MEL-T01 implements personalised cognitive training to alleviate MDD symptoms and improve cognitive performance in MDD subjects.

Arms and interventions:

Arm	Intervention
MEL-T01	Active investigational device MEL-T01 is a digital intervention implemented in a video game with cognitive training components. MEL-T01 is provided together with Treatment As Usual (TAU).
MEL-S01	Active comparator device MEL-S01 is a digital intervention implemented in a video game with reduced cognitive training load. MEL-S01 is provided together with TAU.
TAU	No intervention.

Primary hypotheses:

- MEL-T01 is superior to TAU in alleviating MDD symptoms as measured by the change in subject health questionnaire (PHQ-9) score between time points T0 (before the intervention) and T3 (after a 12-week intervention).
- MEL-S01 is superior to TAU in alleviating MDD symptoms as measured by the change in PHQ-9 score between T0 and T3.
- MEL-T01 superior to MEL-S01 as measured by the change in PHQ-9 score between T0 and T3.

Secondary hypotheses:

- In terms of a score change from T0 to T3,
MEL-T01 is superior to TAU,
and MEL-S01 is superior to TAU,
and MEL-T01 superior to MEL-S01 in:

- reducing depression symptoms as measured by quick inventory of depressive symptomatology (QIDS),
 - reducing rumination as measured by short-version ruminative response scale (RRS),
 - reducing anxiety symptoms as measured by general anxiety disorder (GAD-7),
 - reducing the disability symptoms as measured by sheehan disability scale (SDS),
 - increasing positive emotions as measured by positive valence systems scale (PVSS),
 - and
 - improving well-being as measured by the WHO-five well-being index (WHO-5)
- The effect of the MEL-T01 is mediated by the training dose, as measured by the subject's total game-playing time during the intervention, and evidenced by a positive correlation between MEL-T01 game time and reduction in symptoms as measured by the PHQ-9.
 - The effect of the MEL-S01 is mediated by the training dose, as measured by the subject's total game-playing time during the intervention, and evidenced by a positive correlation between MEL-S01 game time and reduction in symptoms as measured by the PHQ-9.
 - The effects of MEL-T01 on depressive symptoms as measured by PHQ-9 are mediated by positive game experience as measured by the immersive experiences questionnaire (IEQ).
 - The effects of MEL-S01 on depressive symptoms as measured by PHQ-9 are mediated by positive game experience as measured by the immersive experiences questionnaire (IEQ).

Exploratory hypothesis:

- The effects of the MEL-T01 and MEL-S01 on MDD symptoms are sustained in the follow-up period as measured by the change of PHQ-9 scores between T3 and T4.
- The effects of MEL-T01 and MEL-S01 will also emerge in the TAU group once as measured by the change of PHQ-9 between T3 and T4.
- The MEL-T01, MEL-S01, and TAU cohorts are equal in how they are treated for depression over the intervention period aside from the intervention.

- Interventions MEL-T01 and MEL-S01 are not significantly associated with an increase from T0 to T3 in game addiction as measured by the 7-item game addiction scale (GAS).
- The effects of the MEL-T01 and MEL-S01 on depressive symptoms as measured by PHQ-9 are (negatively) mediated by substance abuse as measured by ASSIST-LITE.
- The effects of MEL-T01 and MEL-S01 on depressive symptoms as measured by PHQ-9 are mediated by PTSD symptoms as measured by PTSD checklist for DSM-5 (PCL-5).
- The effects of MEL-T01 and MEL-S01 on depressive symptoms as measured by PHQ-9 are mediated by experiential avoidance as measured by the brief experiential avoidance questionnaire (BEAQ).

Study design:

The subjects ($N = 800$) volunteering to participate in this investigation are diagnosed with MDD and have an on-going mental health treatment contact with a mental health professional. The subjects are recruited through Helsinki and Uudenmaan sairaanhoitopiiri (HUS) psychiatry and Varsinais-Suomen sairaanhoitopiiri (VSSHP) psychiatry as well as online.

The subjects are randomised into three arms with equal probabilities in blocks of six consecutive subjects. Subjects in the MEL-T01 and MEL-S01 arms are engaged in the intervention for 12 weeks while those in the TAU arm are on a follow-up period during these 12 weeks.

After this 12-week period, the subjects in MEL-T01 and MEL-S01 arms enter a 12-week follow-up period and the subjects in TAU arm engage with either the MEL-T01 or MEL-S01 intervention (randomised at T0 with equal probability) for 12 weeks (See Table 1 below).

The subjects are recommended to play the investigational-device game for a total of 48 hours during the 12 weeks of active intervention with a recommended weekly dose of 4 hours. A minimum of 24 hours is needed for inclusion to hypothesis testing. The subjects are limited to a daily maximum of 1.5 hours of game time.

Prior to the intervention, a clinical interview (MINI) is performed via phone to confirm the subject's MDD diagnosis. The subjects' mental health symptoms and well-being are evaluated through online questionnaires five times: before subjects are randomised into one of the three groups (T0), and then 4 (T1), 8 (T2), 12 (T3), and 24 (T4) weeks after the study has begun.

Subject population:**Criteria for inclusion:**

Eligible subjects must fulfil all of the following criteria:

1. Between 18-65 year-old
2. Suffering from major depressive disorder
3. Have an ongoing mental health treatment contact to basic healthcare, specialised healthcare, student healthcare or occupational healthcare
4. Has sufficient eyesight with or without prescription
5. Has a Windows computer with internet connection and mouse
6. Has email and phone number

Criteria for exclusion:

Subjects who fulfil any of the following criteria are excluded from the study:

1. They have threat of self-harm
2. They have addiction to digital games
3. They have psychotic disorders
4. They are pregnant or breastfeeding
5. They have impaired ability in decision making
6. They are prisoner or forensic subject
7. They have neurological disorders such as epilepsy or brain injury

Safety assessments:

MEL-T01 and MEL-S01 have negligible risks to the subject. They are non-invasive cognitive-training-software devices that the subject engages with at home. Pre-clinical evaluation based on internal testing and a pilot study showed no serious adverse effects on the previous version of the game. Adverse effects reported from the population sample of N = 54 were frustration (16.7%) that was almost invariably caused by device deficiencies, i.e., by problems in the technical implementation of the game, boredom due to limited content (14.8%) and anxiety from gameplay pressure (1.8%). Technical implementation of the game has been greatly improved since the previous version hence it is less likely that this kind of adverse effects are reported due to technical problems. More content has been developed into the game.

The version 1.0 made 14.1.2022 has received an approval from the HUS ethical committee (HUS/3043/2021).

Table 1: The overview of the study

Study arms	T0 (Before playing)		T1: T0 + 4 weeks		T2: T0 + 8 weeks		T3: T0 + 12 weeks		T4: T0 + 24 weeks
MEL-T01 intervention		MEL-T01 intervention						Follow-up	
MEL-S01 intervention		MEL-S01 intervention						Follow-up	
Treatment as usual ("TAU")		Treatment as usual						MEL-T01 or MEL-S01 intervention	

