3.2.2 Description

MEL-T01 (“Meliora”), is a digital intervention, a digital therapeutics (DTx) video game, that is installed and operated on a personal computer with a Windows operating system. MEL-T01 implements a closed-loop cognitive training system that looks and feels like an action video game for entertainment. The game is primarily a first-person action video game with puzzle and strategy elements. The player controls the main character in a fictional 3D landscape.

- The game is a single-player game without online features or social interaction with other players.
- The game is free to play and the player cannot make real- or virtual-currency-based purchases in the game.
- The game has 28 levels that the player passes through following a pre-written narrative and unlocking new game features.
- The game’s difficulty is dynamic and adapts to the player's skill level and its changes.

MEL-S01 is derived from MEL-T01 so that the central game mechanics that implement cognitive training are removed. MEL-S01 thus has reduced cognitive training load but remains very similar to MEL-T01, e.g., in terms of action content, progression, and entertainment value (for details, see 3.6.2).

MEL-T01 and MEL-S01 interventions recommend a total of 48 game-play hours during the 12-week intervention period, and at minimum 24 hours during the 12-week intervention period. The subjects are able to play a maximum of 90 minutes per day.

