3.3.1.2 Anticipated AEs

In guidelines for good clinical practice E6(R2) European medicines agency defines adverse events (AE) as: *“Any untoward medical occurrence in a patient or clinical investigation subject administered a pharmaceutical product and which does not necessarily have a causal relationship with this treatment.”*

The subjects may have unanticipated or anticipated adverse events during the study. Below, we have identified anticipated AE that may arise in the use of the MEL-T01 or MEL-S01 software. The list is based on possible negative events that may occur from playing entertainment video games (see Playstation, 2022) that closely resemble the MEL-T01 and MEL-S01 software. The adverse events are:

- Frustration
- Boredom
- Stress
- Eye ache
- Headache
- Dizziness
- Nausea
- Neck pain

- Visual disturbances
- Migraine
- Muscle twitching
- Uncomfortable feelings or ache in hands
- Losing sense of time and space

We take measures to mitigate the anticipated AE. We guide the user to pay attention to ergonomics, ensure sufficient lighting, and keep breaks while playing. Should the user encounter any AE, they are guided to stop playing, and report the AE to the researchers either through the in-game link or email. The information to the subjects is included in Appendix 2 (Tutkittavan tiedote) and the information given to the subject is found in Appendix 6 (Investigator's brochure). For AE reporting procedures, see [3.14](#).

Another risk is the potential addiction that video games may create. To mitigate this risk, we take the following precautions: 1) Digital game addiction is an exclusion criteria for the study. 2) We only recommend playing 45 minutes per day, and the players cannot play the game for more than 90 minutes per day at which point the game locks them out. 3) Our game doesn't include highly addictive features such as so-called loot boxes.

"A very small percentage of individuals may experience epileptic seizures or blackouts when exposed to certain light patterns or flashing lights." (Playstation, 2022). Considering the risk for epileptic seizure, we exclude subjects who have a history of epilepsy from the study to mitigate the risk. We also inform the subject about this (see Appendix 6 - Investigators brochure, 2.2.5.).

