3.6.5 Clinical procedures and diagnostic methods

3.6.5.1 Questionnaires

We use the following questionnaires in gathering data about the subjects. For details regarding the questionnaires, see [3.7.1](#).

- Questionnaire regarding their state of care
- Patient health questionnaire (PHQ-9)
- Quick inventory of depressive symptomatology (QIDS-SR16)
- General anxiety disorder questionnaire (GAD-7)
- Positive valence systems scale (PVSS)
- The ruminative response scale short-version (RRS)
- Alcohol, smoking and substance involvement screening test lite (ASSIST-LITE)
- PTSD checklist for DSM-5 (PCL-5)
- Brief experiential avoidance questionnaire (BEAQ)
- Sheehan disability scale (SDS)
- Well-being index (WHO-5)
- 7 item game addiction scale (GAS)
- Problem gambling severity index (PGSI)

The immersive experiences questionnaire (IEQ, Jennett et al., 2008) measures the subjective experience of being immersed while playing a video game. It has 31 questions on a scale of 1-7, which require the subject to answer according to how they felt at the end of the game. One additional question - "How immersed did you feel?" - on a scale of 1-10, let's the researcher evaluate whether the IEQ reliably reflects the participant's immersive experience. Scores for five immersion factors can then be computed: challenge, control, real world dissociation, emotional involvement and cognitive involvement.

The questionnaire regarding state of care (Appendix 7) determines if there have been any changes in the subject's treatment during the preceding four weeks. If the subject reports changes to have occurred, they are then asked the same questions regarding treatment status as in the background questionnaire part 2: Mental health (see Appendix 7), excluding the open question regarding diagnoses.

The patient health questionnaire (PHQ-9, Kroenke et al., 2001) is a self-report measure of MDD and a component of the longer PRIME-MD diagnostic instrument for common mental disorders. The PHQ-9 scores each of the nine DSM-IV criteria for MDD from "0" (not at all) to "3" (nearly every day), providing a 0-27 severity score of depression.

The quick inventory of depressive symptomatology (QIDS-SR16, Rush et al., 2003) is a self-report measure derived from the 30-item Inventory of Depressive Symptomatology (IDS). It has 16 questions on a scale of 0-3 which assess the severity of depressive symptoms.

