3.7.1.3 In-game questionnaire

The in-game questionnaire occurs after each level achieved by the player. It asks two questions on a seven point scale: 1) does the subject enjoy the game; 2) how difficult did the subject find the game? In addition, the subject is able to mention other aspects considering their play experience. The questions (in Finnish) can be found in Appendix 7 - Data collected in the study.

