3.7.1.4 In-game behaviour

The investigational device feels and displays as a video-game to the subject. Subject navigates in an interacting 3D environment by using keyboard and mouse. The subject's interactions with the game made with keyboard and mouse are stored in game logs. Subject experiences 28 tutorialized game levels that include performing various cognitive tasks that target specific cognitive functions. Purpose of any given game round is to conquer all the monuments. This includes defeating the opposing forces, solving tasks and overcoming challenges.

Performance values from these cognitive tasks, like reaction time, correct answer and execution time, are stored in the game logs and are used in evaluating gameplay performance values. These performance values are evaluated after each game and used for adapting the task difficulty individually to achieve the training effect.

The game includes a narrative and the subject receives feedback from their game progression to support learning. Subject has an avatar that yields magical, non-violent abilities. These include skills that can be used e.g. to alter temporal structure globally or locally, teleport to a location, cast a damaging beam of light or freeze enemies. Use of abilities is stored in game logs. Avatar has also the ability to command up to three friendly allies with defensive and offensive capabilities. Commands assigned to friendly allies are stored in game logs. These performance values are evaluated after each game and used for adapting the task difficulty.

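### Hours of play are labelled training dose in both games, although MEL-S01 carries a reduced training load, and the immersion scale is labelled positive game experience; both mediators need accurate names, and a training-specific dose claim needs a between-arm test

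*Combined protocol and SAP*

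**What the plan says.** Two pairs of secondary hypotheses in 3.1.6, repeated in 3.5, concern how the games work.

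**Dose.** For the investigational device: "The effect of the MEL-T01 is mediated by the training dose, as measured by the subject's total game-playing time during the intervention". For the comparator: "The effect of the MEL-S01 is mediated by the training dose, as measured by the subject's total game-playing time during the intervention". In each arm the stated evidence is a positive correlation between hours and PHQ-9 reduction.

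On the content of the comparator, 3.2.2 says: "MEL-S01 is derived from MEL-T01 so that the central game mechanics that implement cognitive training are removed". The next sentence there describes its training load as reduced. Table 3 in 3.6.2 marks real-time strategy and cognitive tasks as present in MEL-T01 and absent in MEL-S01.

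**Experience.** In both arms the effect is hypothesised to be "mediated by positive game experience as measured by the immersive experiences questionnaire (IEQ"). Section 3.6.5.1 introduces the IEQ as a measure of being immersed in a game and adds: "Scores for five immersion factors can then be computed: challenge, control, real world dissociation, emotional involvement and cognitive involvement". The design rationale in 3.6.1 states the same hypothesis as mediation by how far the player becomes immersed.

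**Related data.** After each level, subjects rate on a seven-point scale, first, "does the subject enjoy the game" (3.7.1.3). For the game logs, 3.7.1.4 says: "Performance values from these cognitive tasks, like reaction time, correct answer and execution time, are stored in the game logs". Neither source is assigned to a mediation hypothesis. Sections 3.7.2 to 3.7.4 give no model, significance level or power for these hypotheses.

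**The concern.** The two devices are built to differ in cognitive training and to match in almost everything else. Total hours count everything a subject does in the game, so an hour of MEL-T01 and an hour of MEL-S01 deliver different amounts of training. The plan nevertheless gives both the same name and accepts a single-arm correlation as evidence in each.

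The protocol itself expects MEL-S01 to help by other routes: 3.2.12.2 names distraction from rumination, pleasure, a sense of competence and a structured day. Hours also respond to things other than training. Payment steps fall at 24 and 48 hours (3.15.1), and coordinators encourage subjects who average under two hours a week (3.10.1). Subjects with a better prognosis may simply play more. Any of these could produce the hypothesised correlation, and it would be reported as mediation by training dose.

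The IEQ problem is one of naming. A result for immersion would be reported as a result for positive experience, while a direct enjoyment rating stands unused. What is at stake is the interpretation of secondary findings, not the primary comparison.

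**Working it through.** **1. The plan's own figure.** Section 3.7.4.1 uses d = 0.40, two-sided alpha 0.0167 and power 0.80. The normal approximation gives n = 2(2.393 + 0.842)²/0.40² = 130.8, so 131 per arm. The exact two-sided t-test gives 132.2, so 133, which agrees with the plan. This size belongs to the primary endpoint. It serves below only as the number per arm.

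**2. Dose: the sections side by side.**

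| Item | MEL-T01 | MEL-S01 |
|---|---|---|
| Mediator name (3.1.6, 3.5) | training dose | training dose |
| Variable | total hours | total hours |
| Real-time strategy (Table 3) | Yes | No |
| Cognitive tasks (Table 3) | Yes | No |

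The name and variable are the same, but the training content is not. A correlation in MEL-S01 alone cannot separate the remaining training load from play time in general.

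**3. How often would prognosis alone confirm the MEL-S01 hypothesis?** Assumptions not in the documents: prognosis induces a correlation r between hours and PHQ-9 reduction, training contributes nothing, and the test is at 0.05. With Fisher's z and n = 133:

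P(reject) = Φ(atanh(r)·√130 − c), with √130 = 11.402 and c = 1.645 (one-sided) or 1.960 (two-sided).

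| r | atanh(r)·√130 | one-sided 0.05 | two-sided 0.05 |
|---|---|---|---|
| 0.10 | 1.144 | 31% | 21% |
| 0.15 | 1.723 | 53% | 41% |
| 0.20 | 2.312 | 75% | 64% |

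**4. What a between-arm comparison does.** The standard error of the difference between two Fisher z values at 133 per arm is √(2/130) = 0.124.

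- Equal confounding in both arms (r = 0.20 and 0.20): the difference is zero, so one-sided rejection stays at 5%.
- Unequal confounding and no training effect (0.20 in MEL-T01, 0.10 in MEL-S01): (0.2027 − 0.1003)/0.124 = 0.826, and Φ(0.826 − 1.645) = 21%. The protection depends on similar confounding in the two arms.
- Power for a real difference (0.35 against 0.20): (0.3654 − 0.2027)/0.124 = 1.312, and Φ(1.312 − 1.645) = 37%.

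These figures compare correlations. They approximate an arm-by-hours slope test when the spread of hours and of PHQ-9 change is similar in the two arms.

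**5. IEQ.** No arithmetic applies. Sections 3.1.6 and 3.5 say positive experience; 3.6.1 and 3.6.5.1 say immersion. None of the five listed factors is named enjoyment or positive affect.

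**The case against.** The strongest reply is that the protocol does not call MEL-S01 free of training. Sections 3.1.6, 3.2.1 and 3.2.2 all describe a reduced load, the safety text in 3.1.6 calls both devices cognitive-training software, and 3.6.1 treats MEL-S01 as an adaptive, closed-loop game. The background sections also measure action-game training in hours. This stands. A reader of the sentence on removed mechanics might infer that MEL-S01 hours cannot be a training dose at all; the documents do not support that. Hours remain a coarse exposure measure in both arms, but not an equal dose.

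Four further objections have force:

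- **Task counts would not cure confounding.** People who play longer complete more tasks, so the percentages in step 3 would apply to task counts at the same r. Section 3.7.1.4 lists performance values, not a count of tasks or time on them, and a cognitive-task dose could exist only for MEL-T01.
- **The IEQ and adverse events.** One factor is real-world dissociation, and the anticipated adverse events include "Losing sense of time and space" (3.3.1.2). A reader might infer that a high IEQ score reflects an adverse event. That rests on a resemblance between names; the item content is not in the document, and no section links the two.
- **Enjoyment or IEQ.** The choice is partly one of preference. Emotional involvement and control may overlap with positive experience. The IEQ is scheduled with PHQ-9 at T1 to T3 in the device arms (Table 5), whereas the number of enjoyment ratings depends on levels reached.
- **Where the mechanistic claim rests.** The plan draws its inference about cognitive training from the randomised comparison of the two devices (3.6.1, 3.6.2), not from these correlations. That inference is untouched.

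None of this removes the shared label, the single-arm evidence rule or the two names for the IEQ mediator.

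**Conclusion.** The concern holds in a limited form. As written, a play-time association in MEL-S01 would be reported as mediation by training dose, although that game carries a reduced training load. The same single-arm evidence in MEL-T01 cannot be read as specific to training either. Under the assumed prognostic correlation of 0.10 to 0.20, the MEL-S01 hypothesis would be confirmed 31% to 75% of the time at one-sided 0.05 (21% to 64% two-sided) with no training effect. These figures illustrate the risk. The documents state neither the correlation nor a test for this hypothesis.

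A between-arm comparison separates general play time from training-specific dose only if confounding is similar in the two arms. The close match between the games makes that plausible but does not guarantee it. The IEQ part is an inconsistency of naming and has no numerical size. The affected hypotheses are secondary, and neither the primary endpoint nor the sample size changes.

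**What to change.** Change 3.1.6 and 3.5, with a matching entry in 3.7.3:

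1. Call total hours game exposure in both arms, and describe a within-arm correlation with PHQ-9 reduction as an exposure association.
2. Allow a training-specific dose claim only if the slope of PHQ-9 reduction on hours is steeper in MEL-T01 than in MEL-S01, tested as an arm-by-hours interaction. State that this assumes similar confounding in both arms.
3. Name the IEQ mediator immersion throughout, as 3.6.1 already does. Report the in-game enjoyment rating as a supplementary measure of positive experience, and say how ratings are summarised when subjects reach different levels.
4. Optionally, add a task-based dose for MEL-T01 as a sensitivity analysis if it can be derived from the logs, noting that it is open to the same confounding.

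The cost is wording, one extra model term and a summary of ratings already collected. The price is power: about 37% in the illustrative case of correlations of 0.35 against 0.20 at 133 per arm, one-sided 0.05. The plan should therefore say that a non-significant interaction does not show that a training-specific dose effect is absent.
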